14.2 Clinical Laboratory Tests

Summaries are provided for the 6 month period by cohort, the extension period by dose, and the entire study period by dose and by cohort. Descriptive statistics for clinical laboratory tests and change from baseline at each scheduled visit based on analysis windows will be presented.

Shift table from baseline to most extreme post-baseline value (including scheduled and unscheduled visits) based on the CTC grading (Grade 0 - 4 where available) will also be generated for each parameter as appropriate. Percentages are based on the number of subjects with each Baseline CTCAE grade.

All non-missing numeric results will be used to determine CTC grade based on CTCAE v4.0. Summary tables consider all lab assessments from baseline up to 30 days post treatment discontinuation. [REDACTED]

[REDACTED]

Lab parameters assessed

Hematology: (counts for differentials)

Blood Chemistry

Urine: Chemistry

Urinalysis

Other labs

For the initial 6-month period, clinical laboratory tests will be presented for each cohort and all cohorts combined. For the extension period, clinical laboratory tests are summarized by dose level. For the entire study period, clinical laboratory tests are summarized by dose level, by cohort, and all cohorts combined.

Figures are provided for each of the lab parameters summarized in the tables (1) by cohort for the first 6 months (2) by dose for the extension (3) for the entire study period by cohort.

[REDACTED]

- [REDACTED]
- [REDACTED]
- [REDACTED]
- [REDACTED]
- [REDACTED]
- [REDACTED]

14.3 Vital Signs

Descriptive statistics for pre-dose vital signs (including systolic and diastolic blood pressure, heart rate, respiratory rate, and temperatures available) at each scheduled visit based on analysis windows will be presented.

Except for respiratory rate and temperature, change from pre-dose to multiple post-dose time points at specific time points will also be summarized.

For the initial 6-month period, mean vital signs will be summarized for each cohort and all cohorts combined.

For the extension period, vital signs are summarized by dose level and summaries.

For the entire study period, vital signs are summarized by dose level, by cohort, and all cohorts combined.

Figures will be summarized for each study period for pre and post dose assessments.

Dot Plot of Change from Pre-dose at Each Time Point for Systolic Blood Pressure/Heart Rate on Day 1 and Day 2 are also provided

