7.4 Summary of Overall Risks and Benefits

7.4.1 Summary of Risks from Nonclinical Studies

7.4.2 Summary of Risks from Clinical Studies

7.4.2.1 111-101

Based on review of the first-in-human Phase 1 study of BMN 111 in healthy adult volunteers, Study 111-101, BMN 111 administered SC daily was well tolerated with doses ranging from 0.5 µg/kg to 15 µg/kg. All AEs were of mild severity, and no SAEs were reported. The most common AE was mild, transient, self-limited orthostatic hypotension, of which the majority of cases were asymptomatic and observed only upon assumption of an upright posture following recumbence. No dose-limiting toxicities were identified outside of these CV findings.

7.4.2.2 111-202

Based on review of this ongoing phase 2 clinical trial, injection site reactions have been identified as risks associated with BMN 111 injections. Hypotension and hypersensitivity reactions are potential risks associated with BMN 111 injections. For a detailed summary of risks, please refer to the current IB.

	BMN 111-202 Amendment 4	Page 32
---	-------------------------	---------

In the phase 2 study BMN 111-202, injection site reactions were the most common AEs reported and are considered as an identified risk associated with BMN 111 injections. The most common injection site reactions across all cohorts included: injection site erythema, injection site swelling, and injection site urticaria. Of note, all injection site reactions have been reported as non-serious and grade 1 in severity, and no subjects have discontinued from the study or permanently discontinued study treatment as a result of the events.

The most important potential risks identified to date include hypotension (and complications related to hypotension and/or tachycardia) and the development of anti-BMN 111 antibodies. Anti-BMN 111 antibodies have the potential to mediate allergic reactions, reduce efficacy, and/or cross-react with endogenous CNP or other undefined agents. Anti-BMN 111 antibodies continue to be monitored in the study. No grade 2 or higher or serious hypersensitivity reactions have been reported to date. Reported adverse events of hypotension have been mild, non-serious, and have resolved without medical intervention. Both these potential risks will continue to be closely monitored.

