9.10.4 Safety Variables

Safety will be evaluated by the incidence of AEs, SAEs, and clinically significant changes in vital signs, physical examination, ECG and ECHO results, imaging, anti-BMN 111 immunogenicity assessments, and laboratory test results (urinalysis, chemistry, hematology). Additionally, imaging, hip monitoring, biomarker, and physical measurement data, including elbow joint range of motion measured with goniometer, will be utilized for safety-related reviews and analysis.

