All other dosing visits	q 15 min (± 5 min); final assessment prior to end of visit (if longer than 1 hr). Includes dose adjustment and follow up visits.			

 Vital sign measurements are taken once per timepoint in a sitting position after at least 5 minutes of rest. Left brachial arm should be the first method of assessment considered, and the same site should be used for measurement of BP in each subject throughout the study. Heart rate should be taken at each timepoint that BP is measured. When blood samples and BP assessments are scheduled at the same time or within the same time window, BP should be measured before blood samples are drawn. If a BP measurement must be taken after a blood draw, ensure adequate analgesia for the blood draw and wait several minutes before measuring BP. Vital signs may be monitored more frequently or for longer duration post-dose as clinically indicated. If a subject has a hypotensive event (or symptoms potentially consistent with hypotension) or a decrease in systolic BP of 20 mm Hg or more from pre-dose systolic BP, blood pressure and heart rate (BP/HR) should be measured and recorded approximately every 15 minutes for the first hour and every 30 minutes thereafter until the systolic BP returns to pre-dose systolic BP (or within the normal range for this subject as defined by PI) and symptoms (if present) resolve. 				

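### The SAP plans no count of children whose systolic pressure falls 20 mm Hg or more after a dose, the protocol's own trigger for repeat monitoring

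*SAP*

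**What the plan says.** **Protocol.** Section 7.4.2.2 ranks the risk high: "The most important potential risks identified to date include hypotension". Section 9.10.4 sets the safety variable: "Safety will be evaluated by the incidence of AEs, SAEs, and clinically significant changes in vital signs". Table 9.10.4.4.1.1, note 7, gives a numeric threshold for a post-dose fall. A hypotensive event, suggestive symptoms, or "a decrease in systolic BP of 20 mm Hg or more from pre-dose systolic BP" means that blood pressure and heart rate "should be measured and recorded approximately every 15 minutes for the first hour and every 30 minutes thereafter until the systolic BP returns". Section 13.4 adds that vital signs will be summarised descriptively and listed.

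**SAP.** Section 14.3 describes pre-dose values at each scheduled visit. For blood pressure and heart rate, "change from pre-dose to multiple post-dose time points at specific time points will also be summarized". In the initial 6 months, "mean vital signs will be summarized for each cohort and all cohorts combined". Section 14 fixes the statistics for numeric safety parameters as n, mean, SD, median, minimum and maximum. Section 14.3 also plans figures of pre- and post-dose values for each study period, and one individual-level plot: "Dot Plot of Change from Pre-dose at Each Time Point for Systolic Blood Pressure/Heart Rate on Day 1 and Day 2 are also provided". Section 14.1.1 tabulates hypotension TEAEs, and events suggestive of hypotension, found by preferred term.

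For laboratory tests, by contrast, Section 14.2 plans a shift table to each subject's most extreme post-baseline value and expressly includes unscheduled visits.

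**The concern.** Safety and tolerability is the primary objective, and hypotension is one of the main risks that the protocol names. The natural question for a dose-escalation study is how many children at each dose had a material fall in pressure after injection. The protocol supplies a threshold and requires extra recorded readings once it is crossed. The SAP then describes pressure time point by time point. It derives no worst fall per child, counts nobody against the threshold, and does not say where the triggered readings go, although these need not coincide with scheduled times.

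If that stands, the only incidence of hypotension by dose will come from adverse event reporting. That depends on investigators' judgement in an unblinded study: the protocol's explicit criteria for turning an abnormal value into an adverse event (Section 10.3.1.4) cover laboratory results only. The gap matters most at dose adjustment, because SAP 2.2 reports that eligible Cohort 1 and 2 children moved up to 15 µg/kg in the extension, and the dot plot stops at Day 2.

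**Working it through.** The plan gives no figure to reproduce: there is no formal sample size calculation and no assumed rate of falls.

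**Inputs from the documents.** Threshold 20 mm Hg (protocol Table 9.10.4.4.1.1, note 7). Cohort size 8 to 10 (SAP 2.4), about 36 children in all (protocol 13.5). Statistics per time point: n, mean, SD, median, minimum, maximum (SAP 14).

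**Assumptions.** A fall is 25 mm Hg, and every other change is zero. These are for illustration only; the documents give no such values.

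**Step 1: scheduled post-dose readings per visit.**
- Days 1 and 2: 120/15 + 120/30 + 240/60 = 8 + 4 + 4 = 16.
- Days 3 and 4: 8 + 4 = 12.
- Other dosing visits: 60/15 = 4, plus a final reading if the visit runs past 1 hour.
- Dose adjustment visits appear in two rows of Table 9.10.4.4.1.1, one giving 12 readings and one giving 4 plus a final one. Those rows must be reconciled.

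**Step 2: does a single fall disappear?** With one child affected, the mean change is -25/n: -3.1 for n = 8, -2.5 for n = 10 and -0.7 for n = 36. The planned minimum is -25 in all three cases. The mean is diluted, but the table still shows the fall.

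**Step 3: can the number of children be recovered?** Take n = 8 and four time points.
- Case A: one child falls 25 mm Hg at all four.
- Case B: four children each fall once, at different time points.

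In both cases every row holds one value of -25 and seven zeros:
- mean = -25/8 = -3.125
- SD = √[((-25 + 3.125)² + 7 × 3.125²)/7] = √(546.875/7) = 8.84
- median 0, minimum -25, maximum 0

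The four rows are identical in the two cases. The counts are 1/8 = 12.5% (exact 95% CI 0.3% to 52.7%) and 4/8 = 50% (15.7% to 84.3%).

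**Step 4: what would a count tell us at this size?** The chance of seeing at least one affected child is 1 - (1 - p)^n. For assumed rates of 5%, 10%, 20% and 30% it is 34%, 57%, 83% and 94% with n = 8, and 40%, 65%, 89% and 97% with n = 10. A count of zero would put the upper exact 95% limit at 36.9% (0/8), 30.8% (0/10) or 9.7% (0/36). The count is coarse within a cohort but interpretable.

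**Step 5: do the other outputs supply the count?**

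| Output | What it gives | Incidence of measured falls by dose? |
|---|---|---|
| Minimum per time point (SAP 14) | At least one child fell | No (Step 3) |
| Dot plot (SAP 14.3) | Individual changes at each time point, Days 1 and 2 | Not after Day 2. As described, it does not link one child's points across times |
| Listing (protocol 13.4) | Raw values | Only if a reader counts by hand |
| Hypotension TEAEs (SAP 14.1.1) | Reported events by preferred term | Of reported events, not of readings |

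**The case against.** The strongest reply is that individual falls are not hidden.

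- A reader might infer that the SAP reports only cohort means and that falls average away. The documents do not support this. The planned minimum would show -25 in the illustration, the Day 1 and 2 dot plots show individuals, and the protocol's listing covers every visit. The SAP does not repeat the listing, but it does not contradict it either, so the rule in protocol 13.7 that the SAP prevails does not remove it.
- A reader might infer that 20 mm Hg is a stopping rule or defines a clinically significant change. It does neither. It is absent from the stopping criteria in protocol 9.1.1.1, Section 9.10.4 does not refer to it, and note 7 lets the investigator define a subject's normal range.
- A reader might infer that falls without symptoms escape adverse event reporting. That is not established. The hypotension search includes preferred terms for decreased blood pressure readings, Grade 1 covers events that are only observed, and in Study 111-101 most of the orthostatic hypotension reported as adverse events was asymptomatic.
- The data monitoring committee reviews safety before each cohort opens, and the clinical pharmacology plan says that it may relate exposure to blood pressure and hypotension.
- The illustration is stylised. Nothing in the documents says that children's falls occur at different times.

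All of this stands, and it limits the point. It does not supply the count. Capture of every measured fall as an adverse event is not guaranteed, and the exposure analyses are optional. Step 3 needs only that summaries by time point do not track which child fell; staggered timing is one of its two cases.

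**Conclusion.** The point holds in a narrow form: the SAP text plans no categorical analysis of the protocol's own 20 mm Hg monitoring trigger, no largest fall per child, and no stated use of the triggered readings. Beyond Day 2 it specifies no individual-level plot, which leaves the protocol's listing. The planned rows cannot separate 1/8 from 4/8 in the illustration, so they cannot give the incidence of measured falls by dose.

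This is a cheap improvement, not a flaw that undermines the safety analysis. It rests on two things: the illustrative values above, and the absence of such a count from table specifications that are not among the documents. SAP 14.1.1 and 14.2 contain redactions and 14.3 shows none. If a count is already specified elsewhere, 14.3 need only refer to it.

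**What to change.** Add one table to SAP 14.3, by cohort, dose level and visit, with dose adjustment visits named. It should give:
- each child's largest post-dose systolic fall from that day's pre-dose value, over all scheduled and unscheduled readings;
- n (%) of children with a fall of 20 mm Hg or more.

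This matches the worst-value approach that SAP 14.2 already takes for laboratory tests. SAP 14 already assigns pre- and post-dose readings on an escalation day to the new dose, so no new attribution rule is needed. State that the window rule in SAP 3.4, which keeps only the assessment nearest the target day, does not drop visits from this table. Compare like with like: a largest fall over 16 readings will tend to exceed one over 4, so rows should be read within visit type.

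Extend the dot plot to dose adjustment days. An exact confidence interval and time to recovery are optional.

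The cost is one table and one plot from readings that the protocol already requires to be recorded, with no change to procedures. The reported hypotension picture may look slightly less favourable.

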14.4 Electrocardiogram and Echocardiogram

Descriptive statistics for pre-dose Electrocardiogram (ECG) results at each scheduled visit based on analysis windows will be presented. For the initial 6-month period, ECG data will be presented for each cohort and all cohorts combined. For the extension period, ECG data are summarized by dose level. For the entire study period, ECG data are summarized by dose level, by cohort, and all cohorts combined.

Both ECG and Echocardiogram (ECHO) results will be listed by subject.

14.5 Hip Monitoring

All hip monitoring assessments will be listed by subject.

14.6 Tanner Stage

All tanner stage assessments will be listed by subject.

14.7 Immunogenicity Analysis

Anti-drug antibody (ADA) tests will be performed using validated immunogenicity assays. Serum samples for ADA tests will be collected at each scheduled visit described in the protocol and amendments. ADA tests will include anti-BMN 111 total antibody (TAb); TAb cross-reactive with endogenous CNP, BNP or ANP; and anti-BMN 111 neutralizing antibody (NAb). NAb testing will not be performed if the TAb is negative. ■

■. Immunogenicity will be summarized for the entire study period, by cohort, and all cohorts combined. Additionally, immunogenicity will be assessed for correlations with measures of safety and efficacy by analyzing ADA positive and negative subjects.

Specifically, change in growth velocity from baseline by ADA status (ADA negative and ADA positive) will be presented using box plots. Incidence of hypersensitivity adverse events (including/excluding ISRs) in ADA negative and positive subjects will be summarized using box plots.

The data conversion rules for immunogenicity analysis are listed in section 18.0.

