- ^k If sleep apnea reading is not accurate, subject may need to repeat assessment. Sleep apnea assessment at early termination visit only if subject discontinues after 18 months.
- ^l Clinical labs (hematology, chemistry, and urinalysis) are all pre-dose draws (samples can be drawn anytime during the visit if there is no drug administration).
- ^m First void upon arrival at the clinic. Screening, Days 1, 10, 15, 22, 29, 43, 85, 127, 183, M8, M10, M12, M15, M18, M21, M24, follow-up 4 wk post-escalation dose, safety follow-up, and early termination. One hr, 2 hr, and 4 hr post-dose collected Days 1, 10, 15, 29, 43, 85, 127, 183, M12, M18, M24 (± 20 minutes for all urine sample time points).
- ⁿ Antibodies: Total and neutralizing anti-BMN 111 immunogenicity samples (serum) will be drawn pre-dose at each time point listed on the SOE. Total immunoglobulin E (IgE) and drug-specific IgE will be drawn on Day 1 and in the event of significant hypersensitivity adverse event (as defined in Section 9.10.4.4.6.2), or at Investigator or Sponsor discretion. The drug-specific IgE sample should be drawn at least 8 hr after the event start time and before the next dose. A sample for total IgE and serum tryptase should be drawn within an hour of the start of the event when possible or during the unscheduled safety visit.
- ^o NTproCNP: Screening; at dosing visits, plasma pre-dose and 4 hr post-dose (± 30 minutes); ANP: plasma pre-dose, 15 min post-dose (± 5 minutes), and 2 hr post-dose (± 15 minutes); cGMP: urine pre-dose, 1 hr post-dose, 2 hr post-dose, and 4 hr post-dose (± 20 minutes for all urine sample time points).
- ^p All bone and collagen biomarkers are drawn pre-dose (samples can be drawn anytime during the visit if there is no drug administration).
- ^q For subjects in the 6-month initial phase, on Days 1, 10, 29, 85, and 183, PK samples are collected pre-dose and at 5 (± 2 min), 15 (± 2 min), 30 (± 5 min), 60 (± 5 min), 90 (± 5 min), 120 (± 5 min), and 180 (± 5 min) minutes post dose. For subjects on a fixed dose in the optional, open-label extension phase, full PK samples will be taken at Months 12 and 24. Partial PK samples will be taken at four time points (pre-dose, 15, 30, and 60 minutes post dose) to estimate exposure and to correspond with immunogenicity assessments. These partial PK draws will take place at Months 8, 10, 15, 18, and 21 with immunogenicity assessments (samples can be drawn anytime during the visit if there is no drug administration).

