13.3.1.4 Immunogenicity Analysis

Immunogenicity will be summarized by change from baseline as well as by study timepoint. Results will be summarized by dose cohort and for all cohorts combined. Additionally, immunogenicity may be assessed for correlations with measures of safety, PK, and efficacy.

	BMN 111-202 Amendment 4	Page 105
---	-------------------------	----------

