14.1 Adverse Events

Adverse events will be coded in accordance with MedDRA version 19.1. A TEAE is defined as any AE that newly appeared or worsened in severity following initiation of study drug administration during the AE reporting period. After informed consent is obtained and the first administration of study drug, all non-serious AEs and SAEs reporting period begins and continues until 4 weeks following either the last administration of study drug or the early termination visit, whichever is longer. If the onset date or end date of an adverse event is partial, the same imputation rules described in Section 9 will be applied.

AEs are summarized by incidence rates and for specific tables also by exposure adjusted incidence rates:

- Incidence rates calculated as number of subjects with the event divided by the number of subjects in the population being assessed
- Exposure-adjusted incidence rates (EAIR) are calculated by dividing the total number of events by the total treatment exposure in the period under assessment for the subjects in the population being assessed. The exposure time for each subject is derived as the time from the date of first dose, to the date of the last dose in the period under assessment.

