18 APPENDIX

Operational Data Conversion Table for Immunogenicity Analysis

Assay	Result Type	Result = "Concentration (Titer Units)"	Pos/Neg for Incidence Table	Numerical Value for Display	Numerical Value for Calculation
Anti-BMN111 TAb	Numeric Titer	Negative Screen	Negative	1	0
		Negative Immunodepletion	Negative	1	0
		Negative Titer (≤ 10)	Negative	1	0
		* Value * (e.g. 20, 30, ...)	Positive	e.g. 20, 30, ...	e.g. 20, 30, ...
		Imputed values - none MRD of assay: 10			
Anti-BMN111 NAb	Numeric Titer	Negative Screen	Negative	1	0
		Negative Immunodepletion	Negative	1	0
		Negative Titer (≤ 5)	Negative	1	0
		* Value * (e.g. 10, 20, ...)	Positive	e.g. 10, 20, ...	e.g. 10, 20, ...
		Imputed values – if TAb negative then impute result as 'Negative' for same study visit MRD of Assay: 5			
ANP Reactivity	Binary	Negative Screen	Negative		
		Negative Immunodepletion	Negative		
		Positive Immunodepletion	Positive		
		Imputed values – if TAb negative then impute result as 'Negative' for same study visit			
BNP Reactivity	Binary	Negative Screen	Negative		
		Negative Immunodepletion	Negative		
		Positive Immunodepletion	Positive		
		Imputed values – if TAb negative then impute result as 'Negative' for same study visit			
CNP-22 Reactivity	Binary	Negative Screen	Negative		
		Negative Immunodepletion	Negative		
		Positive Immunodepletion	Positive		
		Imputed values – if TAb negative then impute result as 'Negative' for same study visit			

	<h2 style="margin: 0;">SART Document Approval Form</h2>
---	---

Study name: BMN 111-202

[figure not shown]

[figure not shown]

Overview

Purpose (Check only 1):

- | | |
|---|---|
|  Final draft SAP
 Revision(s) to the final draft SAP
 Final SAP
 Amendment(s) to the final SAP
 The TOC of TLGs defined by the SAP |  TLG mockups and specifications defined by a SAP
 Revision(s) to the TLG mockups and specifications document after its approval, determined by the Biostatistician to require SART approval
 Request(s) for major changes to mockups and specifications after review of TLG outputs produced for the Dry Run
 Other: |
|---|---|

Comments

Approval

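### SAP 14.7 shows hypersensitivity incidence by ADA status as box plots, which cannot display it, with no readable follow-up adjustment or link between event onset and antibody status

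*SAP*

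**What the plan says.** SAP 14.7 states that "immunogenicity will be assessed for correlations with measures of safety and efficacy by analyzing ADA positive and negative subjects". For safety it specifies one display: "Incidence of hypersensitivity adverse events (including/excluding ISRs) in ADA negative and positive subjects will be summarized using box plots". The period is the whole study: "Immunogenicity will be summarized for the entire study period, by cohort, and all cohorts combined".

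SAP 14.1 gives two ways to summarise adverse events. Incidence is the number of subjects with the event over the number in the group. The other is event-based: "Exposure-adjusted incidence rates (EAIR) are calculated by dividing the total number of events by the total treatment exposure". SAP 14.1.1 applies both to hypersensitivity, with and without ISRs, but not by ADA status.

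Antibody data are repeated and dated. A footnote to the schedules in Protocol 9.1 says "Total and neutralizing anti-BMN 111 immunogenicity samples (serum) will be drawn pre-dose at each time point listed on the SOE", and the SAP appendix (section 18) codes results at visit level, for example "if TAb negative then impute result as 'Negative' for same study visit". Protocol 13.3.1.4 adds only this: "Additionally, immunogenicity may be assessed for correlations with measures of safety, PK, and efficacy".

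**The concern.** There are three gaps in the readable text.

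- **Display.** A box plot needs a distribution of per-subject values. Incidence as SAP 14.1 defines it gives one number per group. The programmer would have to choose another variable, and section 14.7 names none.
- **Follow-up.** Children who decline the extension leave after the Day 208 visit; the others continue to Month 24 or 25. A child followed longer has more chance both of a positive sample and of an event. A crude proportion by ADA status does not separate the two.
- **Timing.** Nothing readable ties the start of an event to antibody status on that date.

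Assessing the impact of immunogenicity on safety is a stated exploratory objective. Protocol 7.4.2.2 lists anti-drug antibodies among the most important potential risks because they may mediate allergic reactions. This is the only readable planned safety output by ADA status, and under Protocol 13.7 the SAP prevails where the two documents differ.

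**Working it through.** The plan gives no rate, effect size or power for this comparison, so there is no figure to reproduce. The first step compares SAP sections. The others are arithmetic on **assumed** values.

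**1. Display against definition.** SAP 14.7 asks for incidence; SAP 14.1 makes that one proportion per group. Two groups give two numbers, with no median or quartiles. A per-subject count or rate could be box-plotted, but neither is named.

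**2. Dilution, if status is ever positive.** Assume a constant baseline rate, 24 months of follow-up for every child, and a true rate ratio RR after seroconversion at mean month T. The apparent ratio is (T + RR × (24 − T)) / 24. Seroconversion spread evenly over Months 1–6, 1–12 or 1–24 gives T = 3.5, 6.5 or 12.5.

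| True RR | T = 3.5 | T = 6.5 | T = 12.5 |
|---|---|---|---|
| 3 | 65/24 = 2.71 | 59/24 = 2.46 | 47/24 = 1.96 |
| 2 | 44.5/24 = 1.85 | 41.5/24 = 1.73 | 35.5/24 = 1.48 |

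This is a rate ratio, which section 14.7 does not plan. On the proportion that it does plan, a ceiling can matter more. With 24-month incidence of 90% in ADA-negative children (conceivable with ISRs included), RR = 3 and seroconversion at month 3, incidence in positives is 1 − 0.1^((3 + 3 × 21)/24) = 1 − 0.1^2.75 = 0.998. The risk ratio is 0.998/0.90 = 1.11.

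**3. Inflation, with no antibody effect.** Let p be the 24-month incidence, and let a share q of ADA-negative children be followed for only 6 months. With a constant rate, 6-month incidence is 1 − (1 − p)^0.25, which is 0.054 for p = 0.20 and 0.159 for p = 0.50. Incidence in negatives is (1 − q) × p + q × (6-month incidence). The false risk ratio is p divided by that.

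| p | q = 0.1 | q = 0.3 | q = 0.5 |
|---|---|---|---|
| 0.20 | 0.20/0.185 = 1.08 | 0.20/0.156 = 1.28 | 0.20/0.127 = 1.57 |
| 0.50 | 0.50/0.466 = 1.07 | 0.50/0.398 = 1.26 | 0.50/0.330 = 1.52 |

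**4. A bare before/after split.** Assume no antibody effect, an event rate k times higher in the first 3 months (rate 1 per month afterwards), and half the children seroconverting at month s. The rate after seroconversion is 1. The rate before it, with never-positive children included, is events over person-months, per child enrolled.

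- k = 2, s = 3: before = 16.5/13.5, ratio 0.82
- k = 2, s = 6: before = 18/15, ratio 0.83
- k = 5, s = 3: before = 25.5/13.5, ratio 0.53
- k = 5, s = 6: before = 27/15, ratio 0.56

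Antibodies would look protective only because seroconversion comes later than the early events. The rows must therefore also be split by time on treatment, and the cut matters. For k = 2 and s = 3, within the first 6 months alone, before = (0.5 × 9 + 0.5 × 6)/(0.5 × 6 + 0.5 × 3) = 7.5/4.5 = 1.67, and the ratio is 0.60. In the extension stratum it is 1.00. If events cluster early, a further cut near month 3 (Day 85) is needed.

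**The case against.** A reader might infer that the SAP uses fixed ever-positive groups, counts events before seroconversion as ADA-positive, and so dilutes an antibody effect. The documents do not support that as a statement of fact. The SAP says only "by analyzing ADA positive and negative subjects", never ever-positive. Blacked-out text stands in the same section just before that analysis and may define positivity; a definition removed there is not missing from the plan. Dilution is not the only possible direction either, as step 3 shows.

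Other points on the plan's side are fair. The objective is exploratory, with no test or decision rule. A box plot of per-subject counts or rates would be legitimate. Exposure-adjusted hypersensitivity rates are planned, and Protocol 13.3.1.4 summarises immunogenicity by timepoint. Significant hypersensitivity events trigger drug-specific IgE, total IgE and tryptase sampling (Protocol 9.10.4.4.6.2). Protocol 7.4.2.2 reports no hypersensitivity reaction of grade 2 or higher, and none that was serious, to date.

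This limits the weight of the point but does not remove it. Section 14.7 names incidence and no per-subject variable, so the mismatch with the box plot stands whatever the blacked-out text says. The exposure-adjusted rates are not planned by ADA status, and the timepoint summary is not linked to event onset.

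**Conclusion.** The point holds in limited form. Two parts rest on readable text and do not depend on how positivity is defined: a box plot cannot show incidence as the SAP defines it, and no exposure adjustment is stated for the ADA comparison. The third part, that event onset is not linked to antibody status, is true of the readable text only.

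The direction and size of any bias are unknown. All the ratios above depend on assumed rate ratios, seroconversion times, incidences and follow-up patterns. They show that the comparison could hide or mimic an effect, not that it will. Early seroconversion with equal follow-up would do little harm (3 becomes 2.71). The consequence is confined to an exploratory safety comparison in about 36 children.

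**What to change.** In SAP 14.7, replace the hypersensitivity box plot with a table giving subjects with events, event counts and exposure-adjusted rates by the SAP 14.1 method.

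- State the rule for an ADA-positive subject, if the blacked-out text does not already do so.
- Assign each event, and the person-time, to TAb status at or before onset: before or after the first positive TAb. Never-positive children contribute to the before row.
- Show the table separately by time on treatment, for example the initial 6 months and the extension, with a further cut at Day 85 if events cluster early.
- Present it with and without ISRs.
- Keep it descriptive. Any confidence interval should allow for repeated events within a child.

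The cost is one dated flag and one table. SAP 14 already assigns each event to the dose on its start date, and antibody results are coded by visit. There are two downsides. Seroconversion is known only to the sampling interval, which runs from 9 days (Day 1 to Day 10) to about three months (Day 85 to Day 183 is 98 days). Strata will also be small, so some rates will rest on very few children.
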